Preprocessing: Post-acquisition preprocessing and statistical analysis of all of the neuroimaging data will be performed using FEAT (FMRI Expert Analysis Tool) Version 5.98, part of FSL (FMRIB's Software Library, www.fmrib.ox.ac.uk/fsl). Functional magnetic resonance imaging (fMRI) blood oxygen level dependent (BOLD) imaging data will be acquired using a standard multi-slice gradient echo planar imaging sequence (TR=2200 ms, TE=35 ms, 64 x 64 matrix, 3 mm isotropic voxels, 271 volumes). Data will be preprocessed using scripting tools from FMRI Expert Analysis Tool (FEAT) Version 5.98, part of FMRIB's Software Library (FSL; www.fmrib.ox.ac.uk/fsl). First non-brain signal will be removed using FSL's BET brain extraction. Scans will be corrected for motion using FSL's linear registration and scans will be spatially smoothed using a Gaussian kernel of 8 mm FWHM. Since head motion can impact functional connectivity analyses, participants with head motion exceeding 0.2 mm will be excluded from the analyses (Power et al., 2012). The "fsl_motion_correction" scripting tool will be used to identify and scrub motion artifacts from each participant's data (Power et al., 2013). Scans will be spatially co-registered with a standardized anatomical template (Montreal Neurological Institute) using a 12 parameter affine transformation (Rorden et al., 2000). **Analysis:** Functional connectivity will be measured using a PPI based approach (Friston et al., 1997). A customized square wave form representing the task (1 = stress condition and -1 = control condition) and the duration of each condition will be convolved with a double-gamma hemodynamic response function. A mask of the seed region will be made using a 12-mm diameter sphere located in the center of the left amygdala using the MNI coordinates (x, y, z = -22, 0, -22). The transformation parameters described above will also be applied to the mask. For each participant and each run of the MIST, the mean corrected and high pass filtered time series of the BOLD signal in the left amygdala will be extracted and used in a single subject whole brain PPI analysis. The PPI model will include (1) the task vector; (2) the time series of the BOLD signal in the left amygdala; (3) a term representing the positive task x seed interaction; and (4) a term representing the negative task x seed interaction. The first level analysis will generate contrast images of the parameter estimates for each of the four regressors. Since the hypotheses associated with Specific Aim 1 explore increases in amygdala - prefrontal cortical connectivity in response to social stress, the group analysis will focus on the positive interaction term. The contrast images of the parameter estimates of the positive interaction term will be entered into a 2nd-level random effects analysis. Unpaired t-tests will be used to test for the following group differences (Hypothesis 1A: CD-PBO vs. HC-PBO) and (Hypothesis 1B: CD-OT vs. CD-PBO). Analyses will be conducted using FMRIBs Local Analysis of Mixed Effects (FLAME 1). Additional analyses comparing (HC-OT vs. CD-OT) will be conducted using an unpaired t-test and applying the appropriate corrections for multiple tests. We will also conduct an exploratory gender analysis between the CD and HC women in the four groups (Domes, Heinrichs, Glascher, et al., 2007; Domes et al., 2010; Potenza et al., 2012). We anticipate that 15-20% of the subjects in each group will be female (n=6/8 per group). We

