Data Analysis: Following preprocessing (described above), within-task data from individual participants will be analyzed with a fixed-effects general linear model (GLM), with each emotion (described below) modeled as a box-car function convolved with a double-gamma hemodynamic response function. The response period at the end of each block will also be modeled as a separate variable to remove effects of explicit decision making and response selection. The GLM procedure is repeated for each voxel with six movement parameters (3 rotation values in radian and 3 translation values in millimeter) included as covariates to control for the influence of head motion on the data. Following first-level analysis, subject-specific contrasts will be entered into second-level, random-effects analyses. Since the hypotheses associated with Specific Aim 2 explore amygdala activity, we will use a region of interest approach (ROI). The BOLD signal from the left amygdala will be extracted using an anatomical mask generated by a 12-mm diameter sphere located in the center of the left amygdala using the MNI coordinates (x, y, z = -22, 0, -22). The percent signal change between the fearful and neutral conditions (contrast of interest) will be calculated for each participant. Separate random-effects one-way analysis of variance tests (ANOVA) will be used to test for the following group differences (Hypothesis 2A: CD-PBO vs. HC-PBO) and (Hypothesis 2B: CD-PBO vs. CD-OT). Since human neuroimaging studies have found that other brain regions play a role in implicit emotional processing, including the right amygdala and insula (Davidson et al., 1999; Shi et al., 2013), secondary analyses will also include these regions. In addition, OT may impact amygdala responding to happy faces (Domes, Heinrichs, Glascher, et al., 2007), therefore group differences in amygdala responding in the happy-neutral contrast may be explored in future analyses. For multiple comparisons that are not part of the hypothesis a priori, the Bonferroni correction will be used. In addition, contrasts of other pertinent baseline characteristics will be performed between groups. If the groups differ significantly on any of these baseline characteristics, the corresponding variables will be used as covariates in the above analyses. The statistical analyses will be conducted using SAS 9.3 software (SAS Institute Inc., Cary, NC, USA).

Power and Sample Size

Specific Aim 1

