Education: Individual variability in cognitive skills (mental arithmetic) may impact the perception of the task as stressful or non-stressful. However, the MIST program includes an algorithm that ensures that the performance of each individual remains below 50%. In addition, groups will be matched by years of education. Trauma Loads/Recall Bias: Childhood trauma has been shown to affect corticolimbic responses to aversive social cues and to OT administration (Dannlowski et al., 2012; Fan et al., 2014). Study participants will complete the CTQ. Scores on the CTQ may be used as covariates in the analyses. Since the CTQ is a retrospective self-report assessment it is subject to recall bias. However, the psychometric properties of the CTQ are well established in healthy controls and cocaine-dependent populations. Sex: Sex differences have been found in stress-related corticolimbic brain activity in CD subjects and in amygdala responding in healthy controls (Domes, Heinrichs, Glascher, et al., 2007; Domes et al., 2010; Potenza et al., 2012). In our experience in recruiting CD subjects for similar research studies we anticipate that only 12-15% of the CD participants will be female, and therefore do not anticipate gender effects from washing out any potential group differences. Abstinence and Years of Use: Frequency and recency of drug use have been shown to affect drug craving and neuroregulatory stress systems (Fox et al., 2005). Subjects will be asked to report their patterns of drug use in the 90 days prior to the study visit. If there are significant group differences in these factors, they will be used as covariates in the analyses. Ovarian Hormones: Menstrual cycle phase, estrogen and progesterone levels can have a significant impact on drug seeking and craving (Evans et al., 2002; Feltenstein et al., 2007). In addition, estrogen and progesterone levels may impact OT effects in corticolimbic brain regions (Choleris et al., 2008; Gimbel et al., 2002). In order to determine the impact of these variables on study outcomes, participants will be asked to complete a menstrual history diary and plasma estrogen and progesterone samples will be analyzed.

C3h. Data Management

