1. Subjects must meet DSM-5 criteria for current (three months prior to study visit) moderate to severe cocaine use disorder. Individuals may meet criteria for marijuana use disorder, but they must not meet criteria for substance use disorder for any other substance (except nicotine and marijuana) within the 60 days prior to study participation. Due to the high comorbidity of alcohol and cocaine use disorder individuals with alcohol use disorder will be included in the study if they do not require medically supervised detoxification.

Exclusion Criteria

1. Subjects meeting DSM-5 criteria for substance use disorder (other than nicotine, cocaine, marijuana or alcohol) within the 60 days prior to study participation.

Healthy Controls

Inclusion Criteria

1. As above.

Exclusion Criteria

1. Subjects meeting DSM-5 criteria for current or lifetime moderate to severe substance use disorder on any drugs of abuse (except nicotine and marijuana).
2. Subjects meeting DSM-5 criteria for marijuana use disorder within the last year.
3. Subjects with a current (past month) major depression or post-traumatic stress disorder.

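### The drug-use covariate rule names no comparison; applied to cocaine-dependent versus control contrasts, it would adjust the cocaine-dependence effect for cocaine use itself

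*Combined protocol and SAP*

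**What the plan says.** Section C3g, under Abstinence and Years of Use, gives its reason, "Frequency and recency of drug use have been shown to affect drug craving and neuroregulatory stress systems", and then its rule: "If there are significant group differences in these factors, they will be used as covariates in the analyses". The rule is mandatory. By contrast, C3g makes childhood-trauma scores only optional covariates, and C3e does the same for nicotine withdrawal.

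The Aim 2 data analysis in C3f (Statistical Methods) has a second trigger. "In addition, contrasts of other pertinent baseline characteristics will be performed between groups", and then: "If the groups differ significantly on any of these baseline characteristics, the corresponding variables will be used as covariates in the above analyses". It does not list the characteristics, and the analyses it follows include 2A (CD-PBO vs HC-PBO) and 2B (CD-PBO vs CD-OT).

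For Aim 1, C3f says: "Unpaired t-tests will be used to test for the following group differences (Hypothesis 1A: CD-PBO vs. HC-PBO"; the same sentence covers 1B, and the group models are run in FLAME 1. A further CD-versus-HC comparison follows: "Additional analyses comparing (HC-OT vs. CD-OT) will be conducted using an unpaired t-test". No drug-use covariate is named for these tests.

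Section 1.1 defines the CD group: "Subjects must meet DSM-5 criteria for current (three months prior to study visit) moderate to severe cocaine use disorder". Controls are excluded for present or past disorder of that severity on drugs other than nicotine and marijuana. On alcohol, in the CD group, "individuals with alcohol use disorder will be included in the study if they do not require medically supervised detoxification". Form 90 (Substance-Related Instruments) records cocaine by value and quantity, and yields percent abstinent days, amount per day and days since last use.

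**The concern.** C3f uses the term group differences for CD-PBO vs HC-PBO as well as for oxytocin versus placebo within CD. An analyst who applies the C3g rule to every such contrast is therefore following the text. In CD versus HC, a significant difference in cocaine use is close to guaranteed by eligibility. Conditioning on it replaces the question in 1A and 2A (do CD subjects differ from controls?) with another (would they differ at equal cocaine use?). Few subjects could inform the second question, and days since last cocaine use has no value for someone who never used.

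Section 5.1 lists amygdala-prefrontal connectivity and the amygdala response to fearful faces among the primary outcomes. Two analysts could follow different sections in good faith and report different results for these. The point concerns cocaine-use measures. Alcohol and marijuana use do not define the CD group, so adjusting for them can be legitimate.

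**Working it through.** **Inputs from the documents.** Power and Sample Size, Aim 1: difference 3.6, RMSE 4.0, so d = 3.6/4.0 = 0.9; 40 per group; type I error 0.05, taken here as two-sided.

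**Assumed inputs.** D is the CD-HC gap in the use measure, in within-group SDs. m is the share of the CD effect that runs through use. The documents give neither, so a range is shown.

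**The plan's own figure.** Unadjusted noncentrality is 0.9 × √(40/2) = 4.02 on 78 df, which gives 98% power. The plan states 80% for 40 per group. About 80% is reached with 20 to 21 per group, so 40 matches the total for two groups. That is a separate matter; 98% is the baseline used below.

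**Does the trigger fire?** With 40 per group, a t-test on the use measure is significant in 91% of trials at D = 0.75, 99% at D = 1 and essentially 100% from D = 2.

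**Cost of adjustment.** With equal groups, the variance inflation from overlap of use with group is VIF = 1 + D²/4. If d = 0.9 is the unadjusted effect, its SD already contains any within-group variation due to use. The slope on use is then 0.9m/D, and the residual SD after adjustment is s = √(1 − (0.9m/D)²). The noncentrality is 0.9(1 − m)/s × √(20/VIF), on 77 df.

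| D | VIF | Noncentrality, m = 0 | Power, m = 0 | s, m = 0.5 | Noncentrality, m = 0.5 | Power, m = 0.5 |
|---|---|---|---|---|---|---|
| 0.75 | 1.14 | 3.77 | 96% | 0.800 | 2.36 | 64% |
| 1 | 1.25 | 3.60 | 94% | 0.893 | 2.02 | 51% |
| 2 | 2.00 | 2.85 | 80% | 0.974 | 1.46 | 30% |
| 3 | 3.25 | 2.23 | 60% | 0.989 | 1.13 | 20% |
| 4 | 5.00 | 1.80 | 43% | 0.994 | 0.91 | 15% |

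**Standard error.** Relative to the unadjusted analysis it changes by s × √VIF. With m = 0 this is 1.07, 1.12, 1.41, 1.80 and 2.24. With m = 0.5 it is 0.85, 1.00, 1.38, 1.78 and 2.22. So precision falls only when the overlap with group outweighs the outcome variance that use explains.

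**Hypothesis 2A.** The Aim 2 power statement labels its effect size of 1.2 as f. Read as d (an assumption), power with m = 0 goes from above 99% to 96%, 84% and 66% at D = 2, 3 and 4, and stays above 99% at D = 1 or less.

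**Randomised contrasts (1B, 1C, 2B).** Any difference in pre-treatment use between arms is due to chance. With two factors tested at 0.05, the trigger fires in 5% of trials (fully correlated factors) to 1 − 0.95² = 9.75% (independent factors).

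**The case against.** The strongest reply is that C3g was written for the CD groups only. Its heading concerns abstinence and years of use, its rationale begins with craving, and some of the measures do not exist for never-users. This is a fair reading and may be what the team intends. But the rationale also cites stress systems, 90-day use is asked of all subjects, and no section limits the rule.

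A reader might infer that C3f and C3g flatly contradict each other. The documents do not support that. FLAME fits a general linear model that can carry covariates, and the plan elsewhere adds covariates outside the sentence that names a test, as it does after the Aim 2 ANOVA. C3g can be read as supplementing the t-test. What remains is an unreconciled specification with no primary result named. For 2A, the test and its own trigger stand together in the Aim 2 section, so the t-test point does not reach it.

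A reader might also infer that adjustment must shrink the estimate and widen its error. Neither is general. The estimate shrinks if the part running through use has the same sign as the total effect and grows if the sign is opposite; the documents do not give the sign. At D = 0.75 with half the effect running through use, the standard error falls.

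Nor does the rule bias the oxytocin contrasts. There it only makes the model depend on chance imbalance, at small cost.

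**Conclusion.** The concern holds as a scope defect with a real consequence. As written, the rule can be applied to CD versus HC. There it is triggered almost automatically for cocaine-use measures and changes what 1A, 2A and the HC-OT vs CD-OT comparison estimate. That conclusion rests on the text and the eligibility criteria alone.

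The size is illustrative. It depends on assumed values of D and m, and on a two-sample approximation to what is, for 1A, a whole-brain cluster-thresholded test. If none of the effect runs through use, the loss is small up to 1 SD of separation (98% to 94%) and large from 2 SD (80% or less). If half does, power is about 64% at best over the range shown. Controls are not barred from all cocaine use, so some overlap between groups is possible. The change should be made; confidence is medium, because the team may already intend the CD-only reading.

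**What to change.** 1. In C3g and in the Aim 2 data analysis, state that cocaine-use measures (frequency, amount, days since last use) are not covariates in the primary CD-versus-HC contrasts. Replace the unnamed baseline characteristics with a list fixed in advance. Candidates already collected are alcohol and marijuana use and the C3b matching factors: age, smoking status and education. State the 1A model in C3f as a FLAME general linear model that can hold them, and word the 2A model to match.
2. In 1B, 1C and 2B, replace the significance trigger with the factors the randomisation balances (gender, smoking status and age; see Medication Administration), and keep the baseline value in 1C. Either leave cocaine-use measures out of the primary model or pre-specify them for a sensitivity analysis. They should not be chosen by a significance test.

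The cost is a few sentences and about three degrees of freedom in the randomised contrasts. No new data are needed.

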1. RISKS TO THE SUBJECTS

1.1 Human Subject Involvement and Characteristics

Admission into the study is open to men and women and to all racial and ethnic groups, aged 18-65. We will scan 160 study participants including (1) cocaine-dependent (CD) individuals (n=80) and (2) healthy control (HC) subjects free of major Axis I diagnoses (n=80). Inclusion/exclusion criteria are listed below:

General Inclusion/Exclusion Criteria

Inclusion Criteria

1. Age 18-65.
2. Subjects must be able to provide informed consent and function at an intellectual level sufficient to allow accurate completion of all assessment instruments.
3. Subjects must consent to remain abstinent from all drugs of abuse (except nicotine) for the three-day period immediately prior to the study visit.
4. Subjects must consent to random assignment.
5. Subjects must have a negative breathalyzer, urine drug screen at the study visit.
6. Subjects must consent to the study visit which includes an outpatient visit to the ASD and completing one functional magnetic resonance imaging (fMRI) scanning session.

Exclusion Criteria

1. Subjects with evidence of or a history of significant hematological, endocrine, cardiovascular, pulmonary, renal, gastrointestinal, or neurological disease including diabetes.
2. Subjects with a history of or current psychotic disorder or bipolar affective disorder.
3. Subjects with current major depressive disorder or post-traumatic stress disorder.
4. Subjects taking any psychotropic medications, including SSRI's or other antidepressants, opiates or opiate antagonists. Subjects taking trazodone or non-benzodiazepene hypnotics for sleep will be included.
5. Women who are pregnant, nursing or of childbearing potential and not practicing an effective means of birth control.
6. Subjects who have a BMI that would preclude them from fitting comfortably in the scanner.
7. Persons with ferrous metal implants or pacemaker.
8. Subjects that are claustrophobic.
9. Subjects with significant psychiatric or medical problems that would impair participation or limit ability to complete the scanning session.
10. Subjects that require maintenance or acute treatment with any psychoactive medication including anti-seizure medications which could potentially interfere with fMRI data acquisition.

Group – Specific Inclusion/Exclusion Criteria

Individuals with Cocaine Dependence

Inclusion Criteria

1. Subjects must meet DSM-5 criteria for current (three months prior to study visit) moderate to severe cocaine use disorder. Individuals may meet criteria for marijuana use disorder, but they must not meet criteria for substance use disorder for any other substance (except nicotine and marijuana) within the 60 days prior to study participation. Due to the high comorbidity of alcohol and cocaine use disorder individuals with alcohol use disorder will be included in the study if they do not require medically supervised detoxification.

Exclusion Criteria

1. Subjects meeting DSM-5 criteria for substance use disorder (other than nicotine, cocaine, marijuana or alcohol) within the 60 days prior to study participation.

Healthy Controls

Inclusion Criteria

1. As above.

Exclusion Criteria

1. Subjects meeting DSM-5 criteria for current or lifetime moderate to severe substance use disorder on any drugs of abuse (except nicotine and marijuana).
2. Subjects meeting DSM-5 criteria for marijuana use disorder within the last year.
3. Subjects with a current (past month) major depression or post-traumatic stress disorder.

1.2 Sources of Materials

Research materials obtained from individual subjects includes structured clinical interviews, questionnaires, blood samples, urine drug screens, urine pregnancy tests, breathalyzer tests, structural and functional MRI scans.

1.3 Potential Risks

Risks associated with the assessment include the possibility that subjects might be upset by questions related to their substance use and psychiatric history. Risks associated with venipuncture may be mild pain and possible bruising. Under certain conditions, participants may experience psychological discomfort from a positive pregnancy test. There are very few potential risks from fMRI itself. There is no exposure to ionizing radiation and the machine and scanning sequences and gradients are approved by the FDA for routine clinical use. Individuals who are claustrophobic might experience anxiety during the scanning procedures. However, we will pre-select individuals who, in general, do not have this problem. A patient may experience some loud noises during the scanning procedure and there is a mild risk of hearing damage if patients are not given hearing protection. Participants may experience psychological discomfort from undergoing the scanning procedure, such as boredom and fatigue. Ferrous objects in the body that are undetected could move during scans. This could lead to tissue damage and hemorrhage. The MIST is designed to induce a stress response, and therefore subjects are likely to experience some psychological discomfort. In addition, cocaine-dependent individuals could experience cocaine craving, therefore cocaine use after the study visit is a potential risk. Adverse effects associated with systemic oxytocin use in pregnancy include seizures, mental disturbances, unexpected bleeding or contraction of the uterus. However, several studies have been conducted in men and women who are not pregnant with intranasal doses between 20 and 60 IU, and no side effects have been reported (Bruins et al., 1992; Fehm-Wolfsdorf et al., 1988). A review by MacDonald and colleagues (2011) also found no adverse outcomes associated with oxytocin dosages of 18-40 IU for short term use in controlled research settings (MacDonald et al., 2011). To date, our research group has administered intranasal oxytocin to over 150 cocaine-dependent individuals and healthy controls with no side effects. These risks are outlined in the informed consent documents.

